**Table 1. Pilot study timeline**

	Month 1	Month 2	Month 3	Month 4	Month 5	Month 6
HREC proposal submission, review and approval	X					
Train study staff in pilot study SOPs	X					
Develop RedCap survey in isiXhosa and pre-test with staff	X					
Recruit and enroll n=200 postpartum women in PrEP-PP study (per eligibility criteria), n=~70/month		X	X	X		
Baseline test for DBS and urine tenofovir levels (all participants)		X	X	X		
Survey (baseline and endline)		X	X	X	X	
Deliver intervention package (SMS, HIVST and biofeedback counseling) to intervention group at day 0, 14 and 30		X	X	X	X	
Study endline: test for DBS and urine tenofovir levels in all participants (at 1 month after follow-up)			X	X	X	
Analysis and dissemination					X	X

## 5. Ethical considerations

The study protocol, informed consent form, all data collection tools, and other requested documents will be reviewed and approved by the University of Cape Town Faculty of Health Sciences Human Research Ethics Committee (UCT-HREC).

### **Informed consent**

The study informed consent for the study and questionnaire are modelled after that used in previous studies and will be delivered in participants' home language (isiXhosa or Afrikaans) by trained interviewers. This study ICF details the purpose of the study, study procedures, and the risks and benefits to mothers that participants may encounter at the second study visit.

Here, study staff will emphasize to participants that:

- Participation is entirely voluntary, and their choice regarding participation will in no way influence the quality of routine medical care for mothers or their infants
- Women may exit the study at any time for any reason without compromising the quality of health care received.

### **Risks**

The potential risks to participants in the study include:

- Risks associated with collection of self-reported behavioural and psychosocial information, related to psychosocial distress raised by questionnaire items involving social support, mental health, or disclosure of HIV status
- Risks due to loss of confidentiality due to study procedures—for instance, in the process of data collection
- Risk associated with asking participants to disclose their status, and potential for interpersonal violence by the partner resultant from the disclosure.

All participants will be informed of these risks, and the strategies to minimize these, as part of the informed consent process. These strategies draw directly from prior experiences conducting research on HIV prevention and treatment in Gugulethu and similar communities across Cape Town.

## **6. Benefits**

**Direct benefit:** The primary direct benefit from participating in this pilot study is that postpartum women in the intervention arm will receive best possible HIV prevention support including ongoing counseling, SMS messages, HIV self-tests, and biofeedback on adherence to improve their PrEP use and prevent HIV acquisition and infant transmission. The proposed intervention is designed to promote adherence to PrEP in high risk women, while minimising contact with the health facility, healthcare workers and study staff through HIVST, phone based SMS counselling, and phone interviews. Therefore, the direct benefit also includes limiting potential COVID exposure in the health facility by postpartum women and their infants, by providing them services that they can use in their home (HIVST, SMS and phone interviews).

**Indirect benefit:** By identifying the optimal strategy for improving PrEP adherence in postpartum women, this study has the potential to lead to improved HIV prevention interventions to protect against HIV acquisition and vertical transmission in HIV-uninfected women and their infants in Cape Town, the Western Cape Province, and across South Africa. Further, if the pilot works and is implemented more widely, it will reduce COVID exposure in the health facility by postpartum women and their infants, by providing them services that they can use in their home.

**Confidentiality:** The following steps will be taken to minimize the risk of any loss of confidentiality throughout study design and conduct.

- All personnel involved in data collection and management will undergo specific training for the study in confidentiality and related patient protection issues.
- Following standard practice, all patient- and study-related information will be kept in locked cabinets at either the study office in Gugulethu or at UCT.
- Anonymous participant identification numbers will be used on all study documents. Collection of participant names and other identifiers will be restricted to informed consent documents, patient tracing materials, and a study identification key, all of which will be kept in a locked cabinet in the study office at Gugulethu and at UCT separate from other study documentation and accessible only by the project coordinator and PI. No CRF will include participant name, including CRF that may reflect HIV status of women or their children.
- All electronic records will be kept in password-protected files. All electronic communications of study data will be through password-protected, encrypted files. All data storage at the University of Cape Town will be within a firewall-protected server.

While efforts will be made to minimize the loss of confidentiality, in the event that staff learn that the participant is a threat to themselves or to others or of possible abuse by partners, the proper authorities will be notified. This exception will be included in all study informed consent forms.

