## **2. Study objectives:**

The objectives of the proposed pilot sub-study are to evaluate the feasibility and acceptability of a package of interventions to improve PrEP adherence in postpartum women.

1. Evaluate acceptability and feasibility of adherence promotion package in women randomized to the intervention arm including:
  - a. SMS: # of messages received, # responded to, feedback from women about responses to messages and utility in improving adherence
  - b. HIV self-testing in women and their partners: # of women who report self-testing at home, and # who report their partners testing (and test results), and feedback from women in surveys about their experience with using self-tests for themselves and partners, and feasibility as reported by study staff to explain HIVST in their counseling
  - c. Integrating urine based lateral flow assays in reporting back adherence levels to PrEP in women: Measured by the time the test takes, correlation with self-reported recent adherence, the feasibility as reported by study staff to read the test and feedback from the woman about the satisfaction and understanding following the bio-feedback
2. Evaluate objective PrEP adherence levels following intervention and compare with standard of care arm:
  - a. Evaluate tenofovir levels in urine assay at 2 weeks and 4 weeks following baseline intervention in intervention arm and compare with standard of care arm at 1 month

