### Inclusion Criteria:

1. Currently enrolled in PrEP-PP study and on PrEP
2. 18+ years old
3. confirmed HIV-negative (confirmed with a 4th generation antigen HIV test)
4. confirmed to be postpartum (1-6 months postpartum)
5. confirmed to currently have a male partner
6. confirmed to have a cell phone that can read and respond to SMS/Whatsapp messages
7. without psychiatric or medical contraindications to PrEP

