**Table 1. Sub-study list of visits and assessments per arm**

Visit	Intervention Arm	Standard of care Arm
Baseline	1. ICF for sub-study 2. Survey 3. HIV self-test for self and partner with counselling 4. Urine TDF test with adherence based counselling	1. ICF for sub-study 2. Survey 3. Invitation for partner testing 4. Urine TDF test (no counselling or feedback)
30 days	1. Endline survey 2. Urine TDF test with adherence based counselling	1. Endline survey 2. Urine TDF test (no counselling or feedback)

**Intervention arm:** Consented, enrolled women in the intervention group (n=100) will receive an adherence promotion intervention package that includes the following visits/assessments:

1. **At baseline:**

- a. HIV self-test for herself and her partner(s) with instructions on how to use, and instructions on how to report the result to the study on the SMS/Whatsapp messages.

- b. Adherence based counseling and feedback from a urine tenofovir test (that measures recent tenofovir in past 48 hours)
- 2. **Weekly:** SMS messaging with counseling and reminders about taking daily PrEP
- 3. **At 2-weeks (extra visit- not part of standard of care):** adherence based feedback and counseling following the urine lateral flow assay

**Standard of care arm:** In the standard of care arm, women will receive normal PrEP-PP services as per study protocol including facility based HIV testing and counselling with a letter to refer their partner for testing in the facility. Women in the standard of care PrEP-PP arm will not receive SMS reminders or messages, nor will they get feedback following the urine assay on their tenofovir levels. Participants will receive standard counselling about importance of adherence, prescription for 3 months of PrEP, and invitations for the study appointment in 4 weeks' time.

**Baseline and endline adherence evaluation (both arms):** All participants, regardless of study arm, will receive urine lateral flow testing of tenofovir levels at baseline and again at 1 month.

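### HIV self-test results are to be reported by SMS/WhatsApp, yet the Confidentiality text says every electronic communication of study data uses password-protected, encrypted files

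*Combined protocol and SAP*

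**What the plan says.** Section 6 (Benefits), in its Confidentiality list, gives a blanket assurance: "All electronic communications of study data will be through password-protected, encrypted files". It names no exception.

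Section 4 (Study procedures), in the baseline list for the intervention arm, provides an "HIV self-test for herself and her partner(s) with instructions on how to use", and then "instructions on how to report the result to the study on the SMS/Whatsapp messages". The arm is planned at 100: "Consented, enrolled women in the intervention group (n=100) will receive an adherence promotion intervention package". The eligibility criteria prepare for this channel by requiring that each woman be "confirmed to have a cell phone that can read and respond to SMS/Whatsapp messages".

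Section 2, objective 1b, lists among the acceptability and feasibility measures the number "of women who report self-testing at home, and # who report their partners testing (and test results".

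The Risks text in section 5 mentions loss of confidentiality, with data collection as its only example. It separately mentions partner violence following disclosure. It does not mention phone messages.

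**The concern.** One section promises a form of protection for all study data in electronic transit. Another sets up a data flow that cannot take that form. The data concerned are HIV results, both the woman's and her partner's, in a group where every participant must have a current male partner and where the protocol itself lists partner violence after disclosure as a risk.

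Two things are at stake. First, staff cannot follow both sentences literally, and anyone relying on the confidentiality text would believe in a safeguard that this route lacks. Second, because the text treats the matter as settled, the available protocol says nothing about handling incoming messages: which study device receives them, who reads them, how a result reaches the database under a study number, or when the message is deleted.

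**Working it through.** The main point involves no calculation and the plan gives no figure to reproduce. The check sets the statements side by side.

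1. **Are the reported results study data?** Yes. Objective 1b includes reported testing by the woman and her partner, and the parenthesis adds results: "who report their partners testing (and test results".
2. **Is the reporting an electronic communication?** Yes. Section 4 directs the result to the study by SMS or WhatsApp, and the eligibility criteria require a phone that can send a reply.
3. **Does a phone message meet the section 6 description?** No. That sentence requires a file protected by password and encryption. A message from a participant's phone is not such a file, whether or not the messaging service encrypts its traffic. The documents do not discuss that, and the conclusion does not need it.
4. **Is there an exception elsewhere?** None appears in the available text. The confidentiality exception that section 6 does state concerns threats to self or others and possible partner abuse, not messaging.
5. **Is the channel recognised as a risk?** Section 5 recognises the harm but does not mention this route to it.

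**Scale.** The plan's own figure is 100 intervention-arm women. The number of results depends on assumptions. If every woman and exactly one partner tested, and every result were texted, the count would be 100 × (1 + 1) = 200. It would be lower with incomplete testing or reporting, and could be higher because the plan allows more than one partner. The weekly reminders sent out by the study are not counted, because they do not transmit study data.

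**Delay under the proposed fix.** If a result were held for the next contact instead of being taken at a call, the longest waits would be 14 − 0 = 14 days (baseline to day 14) and 30 − 14 = 16 days (day 14 to day 30), so about two weeks.

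**The case against.** The best defence is that the section 6 sentence was meant for transfers of datasets between staff or sites. It speaks of files and sits between sentences on electronic record storage and server storage. That may well be the intent. But the sentence says all electronic communications of study data and sets no such limit, so the wording needs correcting even on this reading, and the handling of incoming messages still has to be described.

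A reader might infer more than the documents support:

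- **That participants are wrongly told their data are encrypted.** The consent pages are not available, so what women are told about messaging, and what is arranged for partners' consent, cannot be seen.
- **That the identifier rule is breached because a message shows a phone number.** Section 6 says "Collection of participant names and other identifiers will be restricted to informed consent documents, patient tracing materials, and a study identification key". A phone number fits naturally within tracing materials, and nothing shows that it reaches any other study document.
- **That results travel as readable text.** The content of the instructions is not given. They may already use a code. The text supports only that the format is unspecified.
- **That women's silence would be misread as low uptake of self-testing.** This needs messaging to be the only source of self-test data. Objective 1b also draws on surveys, and the endline survey covers feasibility of the package and can be done by phone.
- **That messaging is the likeliest route of exposure.** Kits taken home for a partner also reveal testing, and the documents rank neither.

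These objections narrow the point but do not remove the conflict between sections 4 and 6.

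**Conclusion.** The point holds as a contradiction in the current text: the safeguard stated in section 6 does not cover the HIV self-test results that section 4 routes through SMS/WhatsApp and objective 1b uses. It concerns the 100 women planned for the intervention arm and whichever partner results they report. The figure of 200 results is an illustration under full testing, one partner each and reporting entirely by message; the conclusion does not depend on it.

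The conclusion rests on two readings: that the word all in section 6 means what it says, and that a result reported for objective 1b is study data. It does not rest on any claim about the consent form, the identifier rule or the security of a particular messaging service.

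This is a data-handling and participant-protection matter with no bearing on randomisation, sample size, error rates or the urine tenofovir comparison. It should still be corrected, because the data are HIV results, the protocol already recognises the harm, and the correction is cheap.

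**What to change.** 1. **Section 4, intervention arm.** Specify that the message carries no HIV result. The woman sends a neutral agreed code or a call-back request. Her own and her partner's results are recorded in REDCap at a call by existing staff, or at the day-14 or day-30 contact already planned.
2. **Section 6, Confidentiality.** Limit the sentence to what is actually done. State the SMS/WhatsApp exception and describe the handling of incoming messages: receiving device, access, entry under the study number, and deletion.
3. **Section 5, Risks.** Add exposure through phone messages to the listed risks, and check that the consent information agrees.
4. **Weekly reminders.** Discreet wording may be offered as each woman's choice. It should not become the default, because reminders about PrEP are part of the intervention under test.

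The cost is revised protocol text, message templates and instruction sheet, with any matching consent wording, plus a few short calls. No new visit, staff post or change in sample size is needed. The drawback is that some results arrive later than they would by text, by up to about two weeks if held to the next contact; using the call-back route shortens this.
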